## LIST OF ABBREVIATIONS

FOCUS	Facilitating and Organizing Communities to Unite for Sustainable Development
IGPC	Initiative for Global Perinatal Care
AE	Adverse Event
(S)AE	(Serious) Adverse Event
SCBU	Special Care Baby's Unit
EC	ethical committee
ENAP	Every Newborn Action Plan
NMR	neonatal mortality rate

## 1. PROJECT SUMMARY

**Rationale:** In order to help premature babies, especially premature babies weighing around 1000 g, reliable equipment to provide thermoneutral environment to minimize energy consumption of the newborn is prerequisite. However, newborn devices in developed countries are very expensive and have a complex structure mostly operated with electric power supply, and high expertise is required to use them. Low cost, simple and sustainable incubator is required in resource limited settings where electric power supply is frequently unreliable. Development of a low-cost, simple and effective incubator has been undertaken by a Japanese perinatal medical device manufacture, ATOM Co,Ltd., and prototypes of the equipment has been now available. The study aims to examine the effectiveness of the incubator in resource limited settings in Special Care Baby's Care Unit (SCBU) in Ola During Children's Hospital.

**Objective:** i .verify the effectiveness in the heat retention of a newly developed incubator for premature babies.

**Hypothesis:** i .Newly developed incubator keeps premature newborn temperature constant.

**Study design:** This is an intervention study at Ola During Children's Hospital

**Study population:** Parturients admitted to Ola During Children's Hospital in Freetown, Sierra Leone.

**Sample size:** During a week period all patients meeting the inclusion and exclusion criteria will be recruited. Based on current rates of admissions in the mentioned services, we expect to recruit at least 6 patients during two weeks data collection period.

**Methods:** Research is conducted on newborns who meet the criteria and are admitted to Ola During Children's Hospital. A patient is accommodated in the newly developed incubator.

All research will be conducted jointly by the Japanese NGO members (a neonatologist and a nurse) and staff at Ola During Children's Hospital. The Japanese neonatologist will always be stationed at the neonatal center during the study period. Local nurses will measure various parameters of hospitalized newborns.

**Main study parameters/primary endpoints:** i . (incubator) Measure body surface temperature and central temperature of newborns in incubator.

**Nature and extent of the burden and risks associated with participation, benefit and group relatedness:** In this study, we are targeting premature babies that have previously been difficult to be saved at Ola During Children's Hospital which may reduce neonatal mortality. Patients are constantly monitored throughout the study to minimize risk. The use of the incubator may result in insufficient heat retention for the patient even though laboratory tests results showed effectiveness of its capability to keep the patient above 37 degree for 3 hours. In order to avoid this problem, a Japanese neonatologist will monitor the patient for 24 hours per day throughout the study period.

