## **2 INSTITUTIONS INVOLVED IN THE PROJECT**

### **2.1 Ola During Children's Hospital**

Ola During Children's Hospital is a tertiary children's hospital in Freetown, the capital city of the country. It has 250 beds and accommodates approximately 1,000 admissions and 3,000 outpatient consultations per month (personal conversation). Special Baby's Care Unit is a ward specifically dedicated to newborn infants in and out of the hospital, where more than 60% of the total deaths of the hospital occur. Three pediatrician and several other junior doctors are treating the patients and one medical doctor is assigned to SCBU. Currently 8 bubble Continuous Positive Airway Pressure devices, donated by UNICEF, are operational. Two open infant warmers are operational.

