#### 6.1.2 Procedure

1. Weigh neonate if weight is > 800 < 2000, and neonate has stable breathing document initial assessment and obtain informed consent from parent
2. Fill the plastic bottle with boiled water and put it in the incubator. We boil clean water by our electric kettle.
3. Assemble incubator
4. Place the bottle in the foil wrap and secure in designated position in the incubator at each end

5. Use hygrometer to confirm that internal incubator temperature is greater than 32 degrees Celsius and less than 37 degrees Celsius.
6. Place neonate inside incubator ensure they are stable.
7. Use data collection sheet to assess each parameter every **15 minutes for the 1st hour** if the baby is stable (maintain the baby's temperature and not change the breathing condition) , we measure the parameter **every 30 minutes**. If the temperature in the incubator exceeds 37° ,open the incubator for 5 minutes and measure the temperature again.
8. Newborn in the incubator always wear a pulse oximeter.
9. Measure without opening the incubator
10. We follow the ODCH doctor's instructions for the interval and methods of feeding.
11. Local nurses observes the newborn in an incubator for 24 hours and then return the newborns to cot.
12. Call a local medical doctor if the newborn has the following problems during our monitoring.: 1) the newborn's respiratory condition deteriorates, 2) the newborn has problem with their feeding patterns and vital signs.
13. Change the hot water to keep the newborn's temperature between 36.5°C and 37.2°C.
14. Wipe once a day with clean water. When replacing the newborn, disassemble the incubator and disinfect with alcohol.
15. measure the water temperature.

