### 3. Performance test results

The results of the performance tests conducted for the warmer are as follows.

- Heat insulation capacity

Pour 2 liters of 38 Degree Celsius water, the average normal body temperature of neonates, into an aluminum can and place it inside of the warmer as a testing model of a neonate. Measure the core temperature of the testing model and count the time until it becomes lowered to 35 Degree Celsius, which is the temperature causing hypothermia, with an ambient temperature and humidity outside of the warmer set at 25 Degree Celsius and 50 % RH respectively. The measurement result is as shown below Figure 1.

[figure not shown]

Figure 1 – The test result obtained from the evaluation on the heat insulation capacity performed by the testing model of a neonate

From Figure 1, it was proven that this product was able to keep warming the testing model of a neonate for a little over 150 minutes with the temperature inside of the warmer being kept at 32 ~30 Degree Celsius during that period.

- Comparison between the core and back temperatures of the testing model  
Due to the nature of this product which supplies heat from under the mattress, the risk associated with the use is a potential scald on the surface skin of the back of a neonate, which the heat source has the closest contact with. To confirm safety, the back and core temperatures of the testing model of a neonate placed inside of the warmer were measured for comparison with an ambient temperature and humidity outside of the warmer set at 25 Degree Celsius and 50 % RH respectively. The measurement result is as shown below Figure 2.

[figure not shown]

Figure 2 – The test result obtained from the comparison made between the core and back temperatures of the testing model of a neonate

From Figure 2, it was proven that since the temperature applied to the back did not exceed the core temperature, there should be no risk of scald with this product.

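### The risk statement's laboratory claim (above 37°C for 3 hours) conflicts with the bench test in the appendix, and no body temperature is set for calling a doctor or marking rescued readings

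*Protocol*

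**What the plan says.** **Risk and mitigation.** The burden-and-risk paragraph of Protocol section 1 admits that the incubator may not retain enough heat. It then cites laboratory tests as showing "effectiveness of its capability to keep the patient above 37 degree for 3 hours", and adds that "a Japanese neonatologist will monitor the patient for 24 hours per day throughout the study period". The Methods paragraph of the same section states: "The Japanese neonatologist will always be stationed at the neonatal center during the study period".

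**Bench evidence.** The Appendix (Performance test results) describes a model filled with 2 litres of water at 38°C, in a room at 25°C. The method was to "count the time until it becomes lowered to 35 Degree Celsius, which is the temperature causing hypothermia". The product was reported "able to keep warming the testing model of a neonate for a little over 150 minutes", with air inside the warmer at 30 to 32°C. Section 6.3.2 separately says that one filling of hot water keeps the incubator warm for more than 3 hours, without giving a temperature.

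**Bedside procedure (section 6.1.2).**
- Step 7 allows half-hourly readings after the first hour "if the baby is stable (maintain the baby's temperature and not change the breathing condition"). It also has the incubator opened for 5 minutes if the air inside exceeds 37°C.
- Step 11: "Local nurses observes the newborn in an incubator for 24 hours and then return the newborns to cot".
- Step 12 has a local doctor called for worsening breathing, or for problems with feeding or vital signs.
- Step 13 has the hot water changed to hold the infant at 36.5 to 37.2°C.

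**Withdrawal.** Section 6.4.1 lets the investigator withdraw an infant for urgent medical reasons.

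**Data sheet.** The table in section 6.1.1 has 11 parameter columns. Armpit temperature is one of them, and there is a row for readings before placement.

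**The concern.** Two things are at stake.

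**Safety.** Parents and the ethics committee are given a laboratory figure as partial reassurance about the one device failure the Protocol predicts. If the figure is wrong, the risk is understated for infants of 800 to 2000 g in a prototype. The procedure sets a temperature limit for incubator air, with an action and a recheck. For the infant's own temperature it gives a target range and one remedy, but no value that prompts a call once that remedy has failed.

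**Interpretation.** The primary hypothesis (section 4.1.3) is that the incubator keeps the infant's temperature constant. If an infant is rewarmed by other means and the sheet does not show it, the later normal readings look like success of the incubator.

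**Working it through.** **1. Laboratory statement against the bench test.**

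Inputs from the Appendix: start 38°C, end 35°C, elapsed time a little over 150 minutes, incubator air 30 to 32°C. The claim in section 1 is above 37°C for 3 hours, that is 180 minutes.

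- The model was at 35°C about 180 − 150 = 30 minutes before 3 hours were up, and 37 − 35 = 2°C below the claimed floor.
- Reading the elapsed time as 160 minutes still puts 35°C 20 minutes before the 3-hour mark.

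This comparison needs no model of cooling.

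**2. When 37°C was crossed.** Figure 1 is not available here, so this step interpolates between the two end points.

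- Constant rate: (38 − 35)/150 = 0.02°C per minute. Then (38 − 37)/0.02 = 50 minutes.
- Exponential cooling toward air at A: k = ln[(38 − A)/(35 − A)]/150, and the time to 37°C is ln[(38 − A)/(37 − A)]/k.

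| Assumption | Time to 37°C (min) | Time from 36.5 to 35°C (min) |
|---|---|---|
| Constant rate | 50 | 1.5/0.02 = 75 |
| A = 30°C | 42.6 | 83.7 |
| A = 31°C | 41.3 | 85.4 |
| A = 32°C | 39.5 | 87.7 |

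The last column uses ln[(36.5 − A)/(35 − A)]/k. With 160 minutes in place of 150, the ranges become 42 to 53 and 80 to 94 minutes.

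The model makes no heat and stood at 25°C ambient. These figures test the laboratory claim and are not forecasts for an infant.

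**3. What the procedure fixes for temperature.**

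| Provision | Acts on | Value given | Next step if it fails |
|---|---|---|---|
| Step 7, opening | Incubator air | 37°C | Remeasure |
| Step 13 | Body temperature | 36.5 to 37.2°C | None stated |
| Step 12 | Vital signs | None | Local doctor called |
| Section 6.4.1 | Urgent medical reasons | None | Withdrawal at discretion |

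The actions exist. What is absent is a body temperature that links step 13 to step 12 or to section 6.4.1.

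**4. The data sheet.** The 11 columns are oxygen saturation, heart rate, respiratory rate, armpit temperature, air temperature inside and outside, water temperature, oxygen inside, milk intake, and humidity inside and outside. None records a call, added warming or removal. With 6 infants, one rescued infant counted as a success is 1/6, or about 17% of the sample.

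**The case against.** **The procedure already responds.** Vital signs ordinarily include body temperature, so step 12 can cover a persistently cold infant. Step 13 is a continuing instruction rather than a single water change, and section 6.4.1 provides a way out. All of this stands. A reader might infer that the Protocol has no action or exit when warming fails, but the text does not support that. The gap is a missing value.

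**The neonatologist is not absent.** Steps 11 and 12 name only local nurses and a local doctor, so a reader might infer that the 24-hour neonatologist monitoring is contradicted. It is not. Section 1 says the work is done jointly and places the neonatologist at the unit throughout, so both can be true. Repeating the role in every step would be drafting preference.

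**Reading frequency.** A reader might infer that half-hourly readings would let an infant cool nearly unseen. Step 7 ties that spacing to a maintained temperature, so an infant losing heat does not qualify for it. At 15-minute spacing, 75 to 88 minutes holds five readings.

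**Other bench evidence.** Section 6.3.2 reports more than 3 hours of warmth. It concerns the incubator and gives no temperature, so it does not support a claim that the patient stays above 37°C.

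**Other records.** Section 7.1.2 mentions checklists and case report forms that are not shown, and sections 6.4.5 and 6.4.6 require all adverse events to be recorded. It therefore cannot be said that a rescue would go wholly unrecorded. What stands is that the printed sheet, which carries the temperature readings, does not mark which of them follow a rescue.

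**Conclusion.** The point holds in three limited parts.

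1. The laboratory statement in section 1 conflicts with the only bench cooling result shown. The model reached 35°C in a little over 150 minutes, where the statement has more than 37°C at 180. This rests on the Appendix end points alone. The 40-to-50-minute crossing of 37°C depends on the assumed cooling curve. Another test may exist that supports the statement, but none is cited.
2. No body temperature is fixed for calling a doctor, or for considering removal, when a water change does not restore 36.5 to 37.2°C.
3. The printed sheet cannot separate temperatures held by the incubator from those restored by other warming. With about 6 infants, one such case could change the conclusion on the primary hypothesis.

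The bench result does not show that infants will become hypothermic in the incubator, because an infant makes heat and the model does not. No sample size or error rate is affected. These are changes the sponsor should make: they concern the Protocol's own stated risk, and they cost little.

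**What to change.** 1. **Section 1:** correct the laboratory statement to match the Appendix (38 to 35°C in a little over 150 minutes, heat-free model, 25°C room), or cite the test that supports it.
2. **Section 6.1.2, step 12:** add a temperature rule. If armpit temperature is below 36.5°C, change the hot water and return to 15-minute readings. Call the on-site neonatologist and the local doctor if it is still below 36.5°C after the water change, or if any reading is 35°C or lower. Likewise call if it stays above 37.2°C. Treatment and removal remain their decision.
3. **Section 6.1.1 data sheet:** record the time of each call, any added warming and any removal. Mark later readings as taken after rescue, so that they do not count as the incubator holding temperature.

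The cost is a few extra readings, calls and entries, and a less favourable laboratory statement. No extra staff are needed: the values and the 15-minute interval are the Protocol's own, and the neonatologist is already stated to be on site. Since the unit's own cover is limited (section 2.1: "one medical doctor is assigned to SCBU"), calling both doctors makes use of a resource already committed.

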## **2 INSTITUTIONS INVOLVED IN THE PROJECT**

### **2.1 Ola During Children's Hospital**

Ola During Children's Hospital is a tertiary children's hospital in Freetown, the capital city of the country. It has 250 beds and accommodates approximately 1,000 admissions and 3,000 outpatient consultations per month (personal conversation). Special Baby's Care Unit is a ward specifically dedicated to newborn infants in and out of the hospital, where more than 60% of the total deaths of the hospital occur. Three pediatrician and several other junior doctors are treating the patients and one medical doctor is assigned to SCBU. Currently 8 bubble Continuous Positive Airway Pressure devices, donated by UNICEF, are operational. Two open infant warmers are operational.

### **2.2 FOCUS1000**

FOCUS 1000 ((Facilitating and Organizing Communities to Unite for Sustainable Development) <http://focus1000.org>) is a Non-Governmental Organization (NGO) in Sierra Leone that is committed to making the best investment in the most crucial period in a child's life: the first 1000 days.

They have a team of over 100 staff members with a diverse background cutting across public health, medicine, nutrition, education, social sciences, environmental sciences and accounting. They also have a pool of over 120 young professionals that we have trained on data collection using digital technology. The organization has a presence in all 14 districts and 149 chiefdoms in Sierra Leone.

### **2.3 IGPC**

IGPC (Initiative for Global Perinatal Care; <https://igpc.jp/>) is a Non-Governmental Organization (NGO) in Japan. We provide medical assistance and education in the fields of obstetrics and neonatology in Honduras, Nepal and Sierra Leone. Our organization has 30 members including medical doctors, midwives, nurses, nutrition specialists, and social scientists. In Sierra Leone, we have been teaching obstetric ultrasound to local doctors and nurses at Princess Christianity Maternal Hospital. Its mission is to deliver perinatal medicine for all mothers and babies across the world.

### **2.4 ATOM MEDICAL**

ATOM MEDICAL is a Japanese corporation (<https://www.atomed.co.jp/>) specialized in medical equipment for peri-natal care medicine. It was founded in 1938 and has been the leading company in Japan as a manufacturer producing maternity and neonatal medical devices. The company has 400 employees and its medical devices have been exported to various countries. The company and IGPC have agreed to develop low-cost and effective equipment for premature newborns in resource limited settings and will provide the prototypes of the equipment for our research.

### **3 BACKGROUND AND JUSTIFICATION**

#### **3.1 Introducing newborn medical devices to developing countries**

We have witnessed a remarkable reduction of the infant mortality rate in the developing countries during the last decade due to internationally concerted efforts to improve access to immunization and primary health care. However, not as much progress in the neonatal mortality rate of these countries has not been achieved as the other indices of maternal and children's health (1). This could be attributed to the fact that perinatal and neonatal medicine requires huge amount of resources, and therefore, can hardly be afforded by the resource-limited countries.

Since Every Newborn Action Plan (ENAP) was launched by World Health Organisation in 2014, the Republic of Sierra Leone has been striving to reduce neonatal mortality rate (NMR), and it was recently rated as one of the top fast progressor countries with highest NMR reductions. However, further efforts should be made to achieve the interim target, namely NMR 15 per 1000 live birth in 2020. Particular emphasis needs to be placed on innovative cost-effective technologies that could function to further boost reductions of NMRs in the country. As was pointed out in ENAP, the leading cause for newborn deaths is prematurity. In order to help these premature babies, especially premature babies weighing around 1000 g, reliable heat retention, respiratory assistance, and nutritional support are essential for their survival.

We have been collaborating with a Japanese manufacture, ATOM MEDICAL Co., Ltd. in order to develop simple and inexpensive perinatal and neonatal medical devices designed for the use in resource limited settings. The purpose of this study is to introduce the simple and cost-effective perinatal and neonatal medical devices in health care facilities in Republic of Sierra Leone. In cooperation with FOCUS1000, we decided to conduct a research at Ola During Children's Hospital.

#### **3.2 The importance of incubator**

Every hour, an estimated 340 babies die in the first week of birth, of preterm birth and asphyxia, which are the most frequently encountered causes for their deaths. Ninety-nine percent of these deaths occur in low- and middle-income countries(1). Compared with adults, newborns are particularly vulnerable to heat loss. Although passive, low-cost approaches such as the Embrace Infant Warmer are available to prevent heat loss of these newborn babes, they lack cooling functions and, therefore, it cannot control their , temperature(2). In many tropical countries, temperatures in the shade can reach >40 °C in the summer, and at this point, an incubator warmer can put babies at risk of hyperthermia. Advanced incubators exist, but they can cost thousands of dollars. The "Neonurture," a design that takes advantage of locally available replaceable parts of automobiles, is not a viable solution for mass production because it is still too complicate to be assembled and expensive (>\$1000) for "bottom of the pyramid" rural users(3). In addition to heat loss, nosocomial

infections are an important cause of infant morbidity and mortality in resource-poor countries, where neonatal deaths toll from sepsis reaches 29% of all neonatal deaths(4),(5). Preterm birth occurs in 11% of live births globally and accounts for 35% of all newborn deaths(6). Because preterm newborns have immature innate and adaptive immunity as compared with term babies, mortality due to inadequate immune system response is high in preterm newborns. Routine medical procedures including respiratory support carry an increased risk of infection and associated longterm morbidity in preterm infants(6). In addition, pediatric respiratory infections appear to contribute to some cases of sudden infant death syndrome(7). We are developing a thermodynamically advanced lowcost incubator suitable for operation in low-resource environments. The incubator features a modular design for multiple purposes. Primarily, it comprises of reusable control modules that have low maintenance requirements and low fixed costs. The incubator features four innovations:

- I. The new incubator is made of vinyl tubes and can be washed. it is reusable and easy to maintain. it can be used many times and is clean
- II. The incubator has a layer of air-contained tubes like a buoyancy ring and has been proven to have a high level of heat retention.
- III. It does not require power supply as it generates heat and humid air from hot water tank stored beneath the bed.
- IV. The cost of the incubator is about 1/100 of the incubator used in developed countries.

